#### **4.0 Study Endpoints\***

This study will focus on assessing the feasibility and acceptability of all protocol components of a pilot pragmatic trial, testing a 6-week telehealth KNA program compared to a KN information only group for older adults with possible MCI in the community and at a senior health clinic to prepare for a full-scale trial. We will use a mixed methods approach using qualitative interviews, quantitative measures of provider's perception of the overall fit of the intervention in the clinic, and of patient intervention attendance and study attrition. Qualitative data from providers and patients will be thematically coded to further examine acceptability and barriers to implementation.

We will also focus on assessing signal of initial effect of the KNA program on important clinical outcomes and adherence relative to a KN information-only condition. Data on clinical outcomes will be extracted or requested from patient health records before and after engaging in the intervention and to compare group differences. Patient participants will also complete assessments in-person, following appropriate COVID-19 precautions, pre- and post-intervention.

We expect that patients in the KNA condition will have higher rates of transferring to the normal range on the RBANS, greater improvements in functional status on the FSQ, and greater improvements in self-reported pain and other health indices. Additionally, we expect higher rates of measurable ketones (trace or higher) in the KNA program compared to KN-only based on daily, at-home urinalysis test strips. Combined, these data will provide important information about the clinical effects of the programs and feasibility of the proposed study components for a larger PCT.

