## 2.0 Objectives\*

- **Objective 1:**

Assess feasibility and acceptability of all protocol components of a pilot pragmatic trial testing a 6-week telehealth KNA program compared to a KN information only group for older adults with possible or pre-MCI in the community and at a senior health clinic to prepare for a full-scale trial.

Specifically, we will examine the feasibility of the recruitment, retention, assessment, electronic health record (EHR) downloads, and intervention delivery methods through the FSU SeniorHealth™ clinic. If we determine it is not feasible to recruit the full sample through this clinic, we will expand recruitment to the community.

We hypothesize that

- *The study protocol (MI-CBT KNA program) will result in high patient retention (90%) and patient attendance of intervention sessions (80%), and*
- *A centralized MI-CBT telehealth delivery approach will be associated with high intervention acceptability ratings from patients and key stakeholders.*
- *MI-CBT KNA program will result in higher adherence to KN compared to the KN information-only group as evidenced by higher levels of ketones at week 6 of the intervention using at-home ketone urinalysis test strips.*

To test these hypotheses, we will use a mixed methods approach using qualitative interviews, quantitative measures of patient satisfaction with the intervention (using the Client Satisfaction Questionnaire) and provider perception of the overall fit of the intervention in the clinic, and of patient intervention attendance and study attrition. Qualitative data from providers and patients will be thematically coded to further examine acceptability and barriers to implementation.

- **Objective 2:**

Assess signal of initial effect of the KNA program on important clinical outcomes and adherence relative to a KN information-only condition.

We hypothesize that *patients in the KNA condition, relative to the KN-only condition, will show 1) higher rates of clinically significant improvements on the RBANS total scale scores, improvements in daily functioning (FSQ), decreases in patient CAIDE risk score, improvements in HbA1C levels and comprehensive metabolic panels, and improvements in self-reported pain using the Rolland-Morris Pain scale, and 2) improved adherence to KN, as evidenced by higher levels of measurable urine ketones in the KNA condition compared to the KN-only condition.*

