*We will also examine the feasibility of using electronic health record (EHR) data as an additional measure of health, pain, and cognitive outcomes.*

To visually examine these hypotheses (as significance testing is not appropriate for a pilot study), we will extract data on clinical outcomes from the EHR to examine patient outcomes before and after engaging in the intervention and to compare group differences.

We expect that patients in the KNA condition will have higher rates of transferring to MCI or normal range on the RBANS and improvements in functional status on the FSQ. Participants in the KNA condition will have reductions in self-reported pain and greater improvements on other health indices. Additionally, we expect higher rates of measurable ketones (trace or higher) in the KNA program compared to KN-only based on daily, at-home urinalysis test strips. Combined, these data will provide important information about the clinical effects of the programs and feasibility of the proposed study components for a larger ePCT.

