## 9.0 Inclusion and Exclusion Criteria\*

### Study Population

Older adults, between the ages of 60-85, and with possible or pre-mild cognitive impairment (MCI) were chosen in order to specifically assess the effect of the intervention on individuals at higher risk for converting to AD. These individuals may observe the greatest cognitive benefits from the intervention, while not requiring a caregiver or significant other to provide assistance or consent. The ages 60-85 were chosen, as this age range is often where early signs of dementia begin to emerge on neuropsychological testing.

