### Inclusion Criteria

To meet eligibility for inclusion in the intervention, participants must be 60-85, meet criteria for possible mild cognitive impairment, have a Telephone MoCA score >12, be English speaking, and have internet access with video conferencing, and report interest in participating in a nutrition intervention. In addition to the criteria above, a subsample of 20 participants will be selected based on self-reported pain on the Rolland-Morris pain scale (A1) of 3 or greater during the past week.

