### Exclusion Criteria

Participants will be excluded if they report any exclusionary health or major psychiatric conditions as determined by their physician at the FSU SeniorHealth clinic (e.g., Type 1 diabetes, schizophrenia etc.), are under-weight based on BMI, have a diagnosable major neurocognitive disorder, or if they report use of prescriptions that may interact with their ability to adhere to the diet (e.g., insulin, MAOIs, immunosuppressant etc.). Those deemed unable to provide informed consent based on the telephone cognitive screener (MoCA<12) will be excluded.

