Preliminary screen. After confirming interest in being contacted about the study, participants will be contacted by a member of the research team and screened for eligibility. This screening will include a telephone MoCA, sections 1 and 4 from the Functional Status Questionnaire, a brief memory complaint scale, self-rated pain during the past week (0-10), and self-reported height, weight, and age. Participants will also be asked to report any restrictive dietary or medical conditions that may make them unable to change their nutrition. Participants will be compensated with a \$5 e-gift card for completing the screening and will be asked to provide their full name and email address to receive the gift card. This contact information will not be retained for future research purposes. All screened participants will be provided with a handout on healthy living designed in collaboration with the SeniorHealth physicians. If participants are eligible, then they will be sent an online consent form, which they will read and review using HIPPA-compliant Zoom with a member of the research team before signing. For participants who are patients at FSU SeniorHealth, the study team will then complete a final eligibility check of the patient's EHR and review with the physician to confirm eligibility and ensure participant safety. For participants who are not patients at FSU SeniorHealth, we will request patients provide a copy of their most recent medical records, including health conditions, medications, and recent lab work – this step will be optional. The study team will determine final eligibility of these patients based on self-reported health conditions or review of the records they provide. Participants who are eligible and consent to participate will have screening data linked with other study data, in order to reduce redundancy in assessment measures. Patients and participants who have previously provided consent to be contacted for research may be called or emailed to assess interest in the study if they are not screened during their normal clinic visits. From this sample, we will recruit up to 60 patients who meet criteria for possible MCI (e.g., MoCA score of 18-25 and some self- or other-reported changes in daily living due to cognition). 20 participants will be selected based on self-reported pain of moderate intensity or greater in addition to the other inclusion criteria. There will be two intervention conditions: 30 patients will be randomly assigned to the 6-week KNA group program and 30 to the KN-only condition. All patients will be given the option of signing up for one of three start dates for the programs, with 10 patients maximum in each group. These conditions are designed to determine whether MI- CBT strategies improve adherence to KN, thereby enhancing the benefits compared to providing KN information alone. Key stakeholders in the clinic will be engaged early in the project to increase buy-in to the intervention and to introduce staff to the project.

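### The RBANS signal is a rate of moving into a better category, which participants already in the normal range cannot show; if everyone is counted, the arm difference is diluted

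*Protocol*

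**What the plan says.** The protocol states the RBANS expectation in three ways.

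- Section 2.0, Objective 2, hypothesis: "higher rates of clinically significant improvements on the RBANS total scale scores". No threshold is given.
- Section 2.0, Objective 2, expectation: "higher rates of transferring to MCI or normal range on the RBANS".
- Section 4.0, Study Endpoints: "patients in the KNA condition will have higher rates of transferring to the normal range on the RBANS".

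Neither transfer statement gives a cut-off or a denominator. Objective 2 adds that the arms will be compared visually, because significance tests are thought unsuitable for a pilot.

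Eligibility rests on other instruments. The inclusion criteria in Section 9.0 require that participants "meet criteria for possible mild cognitive impairment, have a Telephone MoCA score >12, be English speaking", with no upper MoCA limit. Section 12.0 illustrates possible MCI as "MoCA score of 18-25 and some self- or other-reported changes in daily living due to cognition", but only as an example. The study population is described as people "with possible or pre-mild cognitive impairment (MCI) were chosen", and those who "have a diagnosable major neurocognitive disorder" are excluded. The screening call in Section 6.0 uses the telephone MoCA, parts of the FSQ and a memory complaint scale. RBANS first appears at the Time 1 baseline assessment, with no eligibility role. The design is block randomised, and no RBANS stratum is mentioned. Sections 11.0 and 12.0 give 40 to 60 participants, 30 per arm at the maximum.

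**The concern.** A participant whose Time 1 RBANS is already in the normal range cannot transfer into it, whatever the intervention does. Nothing in the entry criteria keeps such people out, and including pre-MCI makes their presence likely. Both transfer wordings share the problem. Widening the target to MCI or normal helps only people who start below MCI, and these should be few given the exclusion of major neurocognitive disorder.

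Two consequences follow if the rate is taken over the whole arm. The visible difference shrinks in proportion to the share already normal. It also moves with any chance difference between arms in that share. Separately, a rate that counts only upward moves credits someone just below the cut who crosses it through measurement error, and does not show the matching downward moves. Since the arms are to be compared by eye, the raw difference in rates would be read directly as the signal for a full-scale trial.

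**Working it through.** The protocol gives no RBANS rate, effect size or power, so there is no stated figure to reproduce.

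**Inputs from the protocol.** 1:1 allocation; n = 30 per arm at the maximum, and n = 20 per arm at the minimum of 40 if allocation stays equal; no RBANS stratification mentioned.

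**Assumptions, not in the protocol.** Share already normal at Time 1, q = 10% to 50%. Transfer rate among those below normal, t = 20% to 60%. All participants in the denominator.

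**1. Dilution.** The rate in an arm is (1 − q) × t. With q equal in both arms, the visible difference is (1 − q) × (difference among those at risk). For a true 20-point difference:

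- q = 10%: 0.9 × 20 = 18 points
- q = 30%: 0.7 × 20 = 14 points
- q = 50%: 0.5 × 20 = 10 points

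**2. Imbalance in the share already normal.** Under random allocation of a fixed number of such people (hypergeometric), the SD of the arm difference in that share is 2 × √[q(1 − q)/(2n − 1)].

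- n = 30: 7.8 points (q = 10%) to 13.0 points (q = 50%)
- n = 20: 9.6 points to 16.0 points

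**3. Effect on the transfer rate.** With equal t in both arms, the distortion is the imbalance in step 2 multiplied by t.

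- n = 30: from 7.8 × 0.2 = 1.6 points to 13.0 × 0.6 = 7.8 points
- n = 20: from 9.6 × 0.2 = 1.9 points to 16.0 × 0.6 = 9.6 points

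**4. Comparison with ordinary noise.** The remaining variance of the rate difference is 2(1 − q)t(1 − t)/n. At n = 30, q = 30%, t = 40%:

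- ordinary part: 2 × 0.7 × 0.24/30 = 0.0112
- imbalance part: (0.4 × 0.1193)² = 0.0023
- total SD: √0.0135 = 11.6 points, of which imbalance is 17% of the variance

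Over the whole grid at n = 30 the total SD is 7.8 to 12.9 points, and imbalance is 2% to 43% of the variance.

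**5. What one draw can do.** Take 18 of 60 already normal. The arms differ by 4 or more such people with probability 0.40, and by 6 or more (for example 12 v 6) with probability 0.16.

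- No effect, t = 40% in both arms, split 12 v 6: 18 × 0.4/30 = 24% v 24 × 0.4/30 = 32%, a spurious 8 points.
- True rates 60% (KNA) v 40%, balanced: 21 × 0.6/30 = 42% v 21 × 0.4/30 = 28%, or 14 points. With 12 already normal in KNA and 6 in KN-only: 18 × 0.6/30 = 36% v 24 × 0.4/30 = 32%, or 4 points. The probability that KNA has 12 or more of the 18 is 0.08.

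**6. After restriction to those below normal.** At n = 30, q = 30%, t = 40%, about 21 per arm remain. The expected difference is no longer diluted or shifted by the split. The SD of the difference is 15.2 points, against 11.6 with everyone counted.

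**The case against.** The strongest reply is that the protocol states no denominator. A rate of transfer into a category can fairly be read as taken among those outside it, and a SAP, not shown here, may say so and may also tabulate downward moves. That stands as far as it goes: dilution and imbalance are conditional on counting everyone. What remains is that Sections 2.0 and 4.0 themselves choose a one-directional category outcome that part of the admitted population cannot show.

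Three stronger readings are tempting, and the protocol does not support them.

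- A reader might infer that the transfer rate is the only cognitive signal. It is not. Objective 2 names improvement on the RBANS total scale, which need not involve crossing into the normal range, and MoCA scores are to be extracted from health records at Time 0 and Time 4.
- A reader might take the imbalance in the share already normal (up to 13 points SD at 30 per arm, 16 at 20) as the error in the result. That imbalance has to be multiplied by the transfer rate, which gives the smaller figures in step 3.
- A reader might call this bias. Under randomisation the imbalance has mean zero, and measurement-error crossings occur in both arms, so neither favours KNA systematically. Dilution is the systematic effect.

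It is also fair to say that the share already normal is unknown. The MoCA example in Section 12.0, if applied as a rule, might make it smaller. Finally, restricting the denominator gains little in signal relative to noise: roughly 14/11.6 = 1.2 before and 20/15.2 = 1.3 after, in a pilot that is mainly about feasibility.

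**Conclusion.** The point holds in a limited form. The two transfer statements describe an event that participants already in the normal RBANS range cannot have, and the entry criteria do not exclude such participants. If all participants are counted, the arm difference shrinks by the share already normal: 20 points becomes 18, 14 or 10 at assumed shares of 10%, 30% or 50%. Chance imbalance adds noise with SD of about 1.6 to 7.8 points at 30 per arm and 1.9 to 9.6 at 20 per arm, under the assumed ranges for the share already normal and for transfer. It can create or mask a visible difference in a single trial, but it is usually smaller than ordinary sampling noise. The wording should be changed because the visual comparison invites a direct reading of this rate and the better outcome is already collected. The feasibility aim is not affected.

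**What to change.** In Section 2.0 (Objective 2) and Section 4.0:

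1. Make baseline-adjusted change from Time 1 in the RBANS total scale score the lead cognitive signal. This is the scale that the Objective 2 hypothesis already names.
2. Define the normal range, and report category transfers only among participants below it at Time 1, giving that number for each arm.
3. Show downward transfers beside upward ones.
4. Reconcile the three RBANS statements, so that the hypothesis, the expectation and the endpoint section name the same outcome and the same target category.

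The cost is a wording change and a different table; all the scores are already to be collected. The drawback is that the transfer rate then rests on fewer people and is less precise: an SD of about 15 points instead of 12 for the arm difference, at 30 per arm with 30% already normal and 40% transfer.

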#### **5.0 Study Intervention/Investigational Agent**

Using a centralized telehealth approach, the KNA program will consist of 7 weekly group meetings across 6 weeks, which will take place via HIPAA-compliant Zoom. The MI-CBT KNA group will be co-led by a clinical psychologist and a nurse practitioner with expertise in nutrition, and the KN information-only group will be led by a nurse practitioner only. Approximately half of each session will be devoted to providing nutrition information and half devoted to psychoeducation, MI activities, and CBT skills. Each group session will be recorded and rated by a trained clinician using a modified MI Coach Rating Scale to measure fidelity to MI-CBT strategies and reviewed with [name], a recognized expert on MI and CBT. These recordings will be stored on a secure College of Medicine network drive and will only be used for the duration of the project and reviewed by the study team for quality control and intervention consistency. Any information from these recordings used for research purposes will be fully de-identified, with qualitative information transcribed and coded by the research team. Participants will be compensated \$20 each week for their time in the study and completion of weekly “homework” (i.e., food logs, ketone logging, and online survey (MSQ, PHQ-9, pain scale, self-reported weight, daily ketone level, self-reported adherence to KN, self-reported barriers and facilitators to adherence, GAS, group cohesion scale, social support scale, and perceived stress scale.))

### **KNA Week 1**

The first group meeting will consist of a 1.5 hour informational and psychoeducational session to introduce participants to the purpose of the group, the ketogenic nutrition goals, and to the MI-CBT model of behavior change in relation to nutrition. Participants will be given a binder that includes weekly goals, handouts on how to maintain KN, including daily recipes and food lists, as well as MI-CBT handouts and worksheets. Participants will be asked to slowly begin reducing their daily net carbohydrate intake to 125g over the first week.

We will provide individualized recommendations for macronutrient intake based on the net carbohydrate weekly goal and participant health information (e.g., sex, weight, height, activity level). Participants will log macronutrient intake in their food logs in order to ensure that approximately 60% of their diet involves healthy fats (e.g., fish, avocado, olive oils), and to begin learning the general macronutrient content of foods they consume. Participants will have the option of completing these food logs online or using paper copies at home. The focus of these first meetings will be on nutritional education and helping participants identify relevant values, goals, and reasons for committing to make healthy changes.

### **KNA Weeks 2-4**

In 1-hour weekly meetings, participants will learn about the CBT model and relevant skills, with assigned homework. Based on feedback from the feasibility trial, the program will emphasize cognitive restructuring and problem-solving as primary skills, while handouts on additional techniques (e.g., distress tolerance, behavioral activation, mindfulness) will be provided as optional.

These skills will help participants identify health goals, manage triggers for unhealthy eating behaviors, and overcome external obstacles to healthy eating. MI will be employed throughout these sessions, through worksheets as well as reflective listening,

summarizing, affirming, and open-ended questions from the group leaders. Participants will be instructed to gradually reduce their net carbohydrate intake across the first 3 weeks of the program in a step-wise fashion (i.e., 125g in week 1, 75g in week 2, 50g or less in week 3) in order to reduce possible adverse responses to the diet (e.g., GI distress, fatigue). Healthy fat intake is a core component of this program, and participants will be provided with ample instruction on ways to increase healthy fat intake while maintaining a healthy balance of macronutrients (e.g., 60% fat, 30% protein, 10% carbohydrates).

### **KNA Weeks 5-6**

In the final two sessions, the focus will shift to emphasize CBT skills practice, maintenance of goals, sustainment of progress, and social support. Participants will make maintenance plans, learn to manage slips, and continue practicing cognitive restructuring skills. The recommended net carbohydrate intake will be reduced to 20g or less these weeks, depending on individual ketone level and macronutrients.

### **KN-Only (Condition 2)**

Participants assigned to the KN-only group will attend a 1.5-hour informational session as a group, which will provide comprehensive information about how to adhere to KN and how to track macronutrients, food intake, and ketone levels. Participants will be provided with the same participant binder as the KNA group with informational handouts and KN recipes, but without the MI-CBT handouts.

Participants will be asked to track their food intake and daily ketone levels, and will be asked to attend a weekly Zoom meeting where they may ask questions about KN and receive additional nutrition information as needed. These optional meetings will be offered for 6 weeks. The structure of this control condition will allow us to examine of the benefits that an MI-CBT group approach provides for increasing adherence to KN and retention in a KN program, compared to KN education only.

